8.1.5 Handling of Dropouts or Missing Data

Missing data for the ITT population will be estimated by multiple imputation and subsequently analyzed. Missing lesion count and IGA data will be derived for the analysis using the method of Markov Chain Monte Carlo (MCMC) multiple imputation. The pattern of missing observations

in each treatment group cannot influence the missing value estimation in the other group because the imputation will be conducted independently for each treatment group.

Last observation carried forward (LOCF) will be used to impute missing data for the efficacy analyses using the Per Protocol (PP) population.

Patients that discontinue from the study due to an AE related to study treatment or documented lack of treatment effect will be included in the PP population. Data for these subjects will not be imputed by multiple imputation or LOCF but rather their data will be imputed with values consistent with their status as treatment failures. For these subjects, values for lesion count and IGA will be imputed such that change from Baseline is zero, meaning the values will be set to the Baseline value. This imputation will be done after the data for all subjects has been through the MI process.

Incomplete start and end dates for medications will be imputed. Other safety data will not be imputed and will be summarized on an observed case basis.

8.1.5.1 Lesion Count Variable Missing Data Imputation

Multiple imputation and subsequent analysis will involve 3 distinct phases with these principal tasks:

1. Create a data set of patients, one for each treatment group, with observed values and those needing estimation by MCMC. The missing lesion count values in each data set will be filled in using the MCMC method 5 times to generate 5 data sets. The resulting data sets for each treatment arm will be combined into one complete data set for each imputation.

Syntax:

```
proc mi data=datain out=dataout seed=&seed. nimpute=5 <options>;  
  where trtpn=(1, or 2);  
  mcmc chain=multiple;  
  var baseline week2 week4 week8 week12;  
run;
```

2. For each complete data set, the variable of interest for Baseline minus the Week 12 value for the week imputed will be computed. Each complete data set will be analyzed as specified for the particular analysis.
3. The results from these analyses will be combined into a single inference using SAS PROC MIANALYZE.

A total of 4 random seeds are needed to impute lesion counts. The following 4 random seeds have been pre-specified by using a random number generator:

- Inflammatory Lesion Counts; S6G5T-3: Seed = 813883085
- Inflammatory Lesion Counts; S6G5T-8 Vehicle: Seed = 2010726808
- Non-inflammatory Lesion Counts; S6G5T-3: Seed = 1326750493
- Non-inflammatory Lesion Counts; S6G5T-8 Vehicle: Seed = 1498908882

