8. STATISTICAL AND ANALYTICAL PLANS

8.1 General Methodology

All statistical processing will be performed using SAS® version 9.3 or later unless otherwise stated. Statistical significance will be based on two-tailed tests of the null hypothesis resulting in p-values of 0.05 or less.

The primary method of handling missing efficacy data will be based on estimation using the method of Markov Chain Monte Carlo (MCMC) imputation. The estimation will be done for each treatment group separately so that the pattern of missingness for one group does not influence the estimation of missing data for another group. Groups of complete datasets following the estimation will be concatenated to form analysis datasets for the comparative

analyses and subsequent imputation result inference with SAS PROC MIANALYZE. Descriptive statistics will also be derived from the multiply imputed datasets.

Sensitivity analyses for the primary efficacy endpoints will use 3 methods. For the lesion count endpoint, the first method will use a repeated measures analysis of covariance (ANCOVA), with treatment, analysis center, visit (i.e., Week 2, Week 4 and Week 8), and treatment group by visit interaction as independent factors and a covariate of Baseline. In this analysis, data from all post-baseline visits will be included with no imputation for missing data.

The second sensitivity analyses will use the model based multiple imputation method to impute missing data for the absolute change at Week 12.

The third sensitivity analysis will involve a tipping point analysis.

Similar methods for the dichotomized IGA will involve a repeated measures logistic regression model and a model based multiple imputation and tipping point analysis.

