8.1.5.2 IGA Missing Data Imputation

A similar procedure will be used for the analyses based on proportion of IGA successes wherein the ANCOVA analysis is replaced with a logistic regression analysis. Specifically, missing IGA values from which the dichotomized IGA is derived will be estimated by MCMC. The pattern of missing observations in each treatment group cannot influence the missing value estimation in the other because the imputation is being conducted independently for each treatment group.

The missing IGA values will be derived for the analysis using the method of MCMC multiple imputation. Multiple imputation and subsequent analysis will involve 3 principal tasks:

1. Create a data set, one for each treatment group, of patients with observed values and those needing estimation by MCMC. The missing IGA values in each data set will be filled in using the MCMC method 5 times to generate 5 data sets. The resulting data sets for each treatment arm will be combined into one complete data set by imputation.

Syntax:

```
proc mi data=datain out=dataout seed=&seed. nimpute=5 <options>;  
  where trtpn=(1, or 2);  
  mcmc chain=multiple;  
  var baseline week2 week4 week8 week12;  
run;
```

2. For each complete data set, the dichotomous success rate (clear or almost clear with a 2-point change from Baseline) will be computed. The estimated global values will be rounded to the nearest integer value prior to evaluating the success rate. Each complete data set will be analyzed with a logistic regression with factors of treatment group and analysis center.
3. The results from these analyses will be combined into a single inference using SAS PROC MIANALYZE.

The following 2 random seeds have been pre-specified by using a random number generator:

- IGA; S6G5T-3: Seed = 377388888
- IGA; S6G5T-3 Vehicle: Seed = 1174190226

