8.1.5.3 PRE-FACE Missing Data Imputation

The same procedure will be used for the analyses based on proportion of PRE-FACE item 1 (pimples) and item 5 (embarrassment) successes as the IGA success. Specifically, missing PRE-FACE items 1 and 5 values from which the dichotomized versions are derived will be estimated by MCMC. The pattern of missing observations in each treatment group cannot influence the missing value estimation in the other because the imputation is being conducted independently for each treatment group.

The missing PRE-FACE items 1 and 5 values will be derived for the analysis using the method of MCMC multiple imputation. Multiple imputation and subsequent analysis will involve 3 principal tasks:

1. Create a data set, one for each treatment group, of patients with observed values and those needing estimation by MCMC. The missing PRE-FACE items 1 and 5 values in each data set will be filled in using the MCMC method 5 times to generate 5 data sets. The resulting data sets for each treatment arm will be combined into one complete data set by imputation.

Syntax:

```
proc mi data=datain out=dataout seed=&seed. nimpute=5 <options>;  
  where trtpn=(1, or 2);  
  mcmc chain=multiple;  
  var baseline week2 week4 week8 week12;  
run;
```

2. For each complete data set, the dichotomous success rate (at least a 4-point reduction from Baseline) will be computed. The estimated global values will be rounded to the nearest integer value prior to evaluating the success rate. Each complete data set will be analyzed with a logistic regression with factors of treatment group and analysis center.
3. The results from these analyses will be combined into a single inference using SAS PROC MIANALYZE.

The following 4 random seeds have been pre-specified by using a random number generator:

- PRE-FACE Pimples Scores; S6G5T-3: Seed = 1597410322
- PRE-FACE Pimples Scores; S6G5T-3 Vehicle: Seed = 466920922

- PRE-FACE Embarrassment Scores; S6G5T-3: Seed = 288784276
- PRE-FACE Embarrassment Scores; S6G5T-3 Vehicle: Seed = 1746263137

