8.7.2.1.2 Model Based Multiple Imputation

The second sensitivity analysis will use the model based multiple imputation method to impute missing data for the absolute change in lesion counts at Week 12. The multiple imputation will involve 3 principal tasks:

1. Missing values will be filled in 5 times to generate 5 complete data sets. The imputation model used will be an ANCOVA with factors of treatment group and analysis center, and a covariate of Baseline lesion count (i.e., the imputation model will be the same as the analysis model).

Syntax:

```
proc mi data=datain out=dataout seed=&seed. nimpute=5 <options>;  
  class trtpn sitegr1;  
  var trtpn baseline sitegr1 week12;  
  monotone logistic (sitegr1=trtpn baseline);  
  monotone reg (week12=trtpn baseline sitegr1);  
run;
```

2. Each complete data set will be analyzed with an ANCOVA with factors of treatment group, and analysis center, and a covariate of Baseline lesion count. Appropriate modifications will be made should the analysis be based on a non-parametric method.
3. Results from these analyses will be combined into a single inference.

Two random seeds will be needed to impute the inflammatory and non-inflammatory lesion counts. The following random seed has been pre-specified by using a random number generator:

Inflammatory Lesion Count Seed= 1098696156

Non-inflammatory Lesion Count Seed= 1003722056

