8.7.2.1.3 Tipping Point

A tipping point analysis of the primary endpoints will be performed as a sensitivity analysis for the handling of missing data. The multiple imputation datasets used for the primary analyses will be used for the tipping point analyses for lesion counts. To perform the tipping point analysis, the imputed values from the multiple imputation datasets for only the E-BPO/E-ATRA cream arm will be adjusted, by adding a constant (shift value) to the lesion counts. Change from Baseline will then be recalculated with the changed imputed values. The shifted multiple imputed datasets will then be analyzed as described in the primary endpoint section. This will then be repeated by adding the constant again to create another new shifted multiple imputed dataset and that dataset will be analyzed. The resulting point estimates and p-values associated with each shift value will be presented in order to assess the magnitude of the shift value required to “tip” the p-value greater than 0.05.

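### Five imputations leave avoidable Monte Carlo error in the ITT multiple-imputation analyses; a larger number would steady borderline gated secondary steps and the lesion-count tipping shift at almost no cost

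*SAP*

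**What the plan says.** - **Lesion counts (SAP 8.1.5.1).** Missing counts are "filled in using the MCMC method 5 times to generate 5 data sets". These counts supply two of the three co-primary endpoints, the Week 12 percent changes, and the Week 8 and Week 4 absolute changes.
- **IGA (SAP 8.1.5.2).** "The missing IGA values in each data set will be filled in using the MCMC method 5 times to generate 5 data sets".
- **PRE-FACE items 1 and 5 (SAP 8.1.5.3).** "The missing PRE-FACE items 1 and 5 values in each data set will be filled in using the MCMC method 5 times".
- **Model-based sensitivity analyses (SAP 8.7.2.1.2 and 8.7.2.2.2).** "Missing values will be filled in 5 times to generate 5 complete data sets", for both lesion counts and IGA.
- **Seeds.** All are listed in the SAP. For lesion counts: "The following 4 random seeds have been pre-specified by using a random number generator".
- **Tipping point for lesion counts (SAP 8.7.2.1.3).** The imputed data sets of the primary analysis are reused, with a growing shift added to the imputed active-arm values, "in order to assess the magnitude of the shift value required" to take p above 0.05.
- **Decision rule (SAP 8.1).** "Statistical significance will be based on two-tailed tests of the null hypothesis resulting in p-values of 0.05 or less". Under SAP 8.1.8 the secondary endpoints are tested in a fixed order, and the first non-significant step ends the sequence.

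Protocol 17.4.6 and 17.4.7 also state five. Neither document gives a reason for five, an expected missing rate, or a planned check of Monte Carlo error.

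**The concern.** A pooled estimate from m imputations carries simulation noise that shrinks with 1/m. With m = 5, the same trial data analysed under a different seed would give a visibly different p-value. That is harmless when the result is far from 0.05, but the plan has two places where results may lie near it.

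The first is the gated secondary sequence. SAP section 9 states power only for the three co-primary endpoints. None is stated for the PRE-FACE responder steps or the Week 8 and Week 4 lesion-count steps, so a borderline p-value there is plausible. One step that fails through imputation noise removes every later claim.

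The second is the lesion-count tipping-point analysis. It searches for the shift at which p crosses 0.05, so by construction it reports a number taken where the noise matters most.

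**Working it through.** **Inputs from the documents.** Two-sided alpha of 0.05; m = 5; 280 and 140 patients (2:1). Planning values from SAP section 9: inflammatory difference 4.5 with SD 10.0, non-inflammatory difference 10.0 with SD 19.0, IGA success 33.3% against 12.6%.

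**Assumptions.** The fraction of missing information (FMI) is not given. I use 10% and 20%.

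**Step 1: the plan's own figure.** No stated figure depends on m, but the power claim matters for what is protected. For inflammatory lesions at 99% power, vehicle n = 1.5 × 10² × (1.960 + 2.326)² / 4.5² = 136.1, so 137, with 274 on active and 411 in total. This matches the SAP.

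**Step 2: distance of the co-primary tests from the boundary.** With 280 and 140 patients, √(1/280 + 1/140) = 0.1035. The expected complete-data z at the planned effects is:

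- inflammatory: 4.5 / (10 × 0.1035) = 4.35
- non-inflammatory: 10 / (19 × 0.1035) = 5.08
- IGA: pooled rate (2 × 0.333 + 0.126)/3 = 0.264, so 0.207 / (√(0.264 × 0.736) × 0.1035) = 4.54

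All are well above 1.96.

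**Step 3: Monte Carlo SD of the pooled z.** Approximately √(FMI/m).

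| FMI (assumed) | m | SD of z | z = 2.10 ± 2 SD | p range | Efficiency 1/(1 + FMI/m) |
|---|---|---|---|---|---|
| 10% | 5 | 0.141 | 1.82 to 2.38 | 0.017 to 0.069 | 0.980 |
| 10% | 50 | 0.045 | 2.01 to 2.19 | 0.029 to 0.044 | 0.998 |
| 20% | 5 | 0.200 | 1.70 to 2.50 | 0.012 to 0.089 | 0.962 |
| 20% | 50 | 0.063 | 1.97 to 2.23 | 0.026 to 0.048 | 0.996 |

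At z = 2.10 the p-value without Monte Carlo error is 0.036. With five imputations the ±2 SD range straddles 0.05; with 50 it does not, at either FMI.

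**Step 4: simulation check.** N = 420, 2:1, five visits, monotone dropout, imputation by arm, ANCOVA with baseline and 20 centers, Rubin pooling. Visit correlations, visit SDs, number of centers and dropout are assumptions. The FMI came out at about 7.5%, 12% and 17% for 10%, 15% and 20% missing at Week 12.

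When the large-m p-value is 0.04:

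| Missing | Share of seeds with p > 0.05: m = 5 | m = 50 | m = 100 |
|---|---|---|---|
| 10% | 29% | 1% | 0% |
| 15% | 37% | 4% | 1% |
| 20% | 42% | 9% | 3% |

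Lesion-count tipping shift, central 95% over seeds, one simulated trial per dropout rate:

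| Missing | m = 5 | m = 50 |
|---|---|---|
| 10% | 31 to 38 lesions | 34 to 36 |
| 15% | 5 to 10 | 7 to 8 |
| 20% | 14 to 18 | 16 to 17 |

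With data generated under the planned inflammatory effect (again one trial per rate), the largest p over 300 seeds at m = 5 was 0.00015, 0.023 and 0.0022. No conclusion changed.

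**The case against.** The strongest reply is that five imputations are legitimate. Rubin's total variance includes a term for finite m and the degrees of freedom adjust for it, so type I error is not inflated. The listed seeds make the result reproducible and rule out choosing a favourable one after unblinding. All of this stands. A reader might infer that the p-values are invalid or open to manipulation; the documents support neither. Fixed seeds do not, however, remove Monte Carlo error: they commit the trial to one draw.

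Three limits on scope also stand:

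- A reader might infer that every tipping point depends on the seed. The IGA version (SAP 8.7.2.2.3) enumerates all combinations of imputed successes, so its boundary is not random; only the overlaid average comes from imputation.
- The per-protocol analyses use LOCF (SAP 8.1.5), and the repeated-measures sensitivity analyses use no imputation (SAP 8.7.2.1.1 and 8.7.2.2.1). Neither is touched.
- The lesion-count tipping point is a robustness display and not a decision rule.

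On size, the FMI is assumed, the z = 2.10 example is deliberately placed near the threshold, and nobody can say how likely a secondary step is to land there. Because earlier visits enter the imputation model, FMI should fall below the missing fraction, as it did in the simulation. If dropout accumulates, Weeks 4 and 8 should have less missing data than Week 12. These points reduce the expected impact without removing it.

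**Conclusion.** The point holds as a cheap precision improvement. In the ITT multiple-imputation analyses, m = 5 costs about 2% to 4% in efficiency at an assumed FMI of 10% to 20%, against less than 0.5% at m = 50. It leaves a seed-to-seed SD in z of about 0.14 to 0.20. That is enough to decide a borderline gated step and to move the lesion-count tipping shift by several lesions: the 95% spread was about 4 to 7 lesions in the simulated trials, against 1 to 2 at m = 50.

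It would be tempting to conclude that the co-primary results are at risk. At the planned effects they are not: expected z is 4.35 or more, and no simulated conclusion changed. That protection depends on the planned effects being roughly right, and all the sizes above depend on a missing-data rate that the documents do not give.

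**What to change.** Set nimpute to at least 50, for example 100, in both text and syntax of SAP 8.1.5.1, 8.1.5.2, 8.1.5.3, 8.7.2.1.2 and 8.7.2.2.2. Keep the seeds already listed. The lesion-count tipping point in 8.7.2.1.3 then inherits the larger set without further change.

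Record the change in SAP section 10, because protocol 17.4.6 and 17.4.7 also state five. SAP section 2 lets the SAP supersede the protocol and be updated until the blind is broken. It also says an amendment will be considered for major differences, such as changes affecting the primary-endpoint analysis, so the sponsor should note its decision on that.

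The cost is computing time and one documented departure from the protocol. No data, endpoint or analysis model changes.

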8.1.5.2 IGA Missing Data Imputation

A similar procedure will be used for the analyses based on proportion of IGA successes wherein the ANCOVA analysis is replaced with a logistic regression analysis. Specifically, missing IGA values from which the dichotomized IGA is derived will be estimated by MCMC. The pattern of missing observations in each treatment group cannot influence the missing value estimation in the other because the imputation is being conducted independently for each treatment group.

The missing IGA values will be derived for the analysis using the method of MCMC multiple imputation. Multiple imputation and subsequent analysis will involve 3 principal tasks:

1. Create a data set, one for each treatment group, of patients with observed values and those needing estimation by MCMC. The missing IGA values in each data set will be filled in using the MCMC method 5 times to generate 5 data sets. The resulting data sets for each treatment arm will be combined into one complete data set by imputation.

Syntax:

```
proc mi data=datain out=dataout seed=&seed. nimpute=5 <options>;  
  where trtpn=(1, or 2);  
  mcmc chain=multiple;  
  var baseline week2 week4 week8 week12;  
run;
```

2. For each complete data set, the dichotomous success rate (clear or almost clear with a 2-point change from Baseline) will be computed. The estimated global values will be rounded to the nearest integer value prior to evaluating the success rate. Each complete data set will be analyzed with a logistic regression with factors of treatment group and analysis center.
3. The results from these analyses will be combined into a single inference using SAS PROC MIANALYZE.

The following 2 random seeds have been pre-specified by using a random number generator:

- IGA; S6G5T-3: Seed = 377388888
- IGA; S6G5T-3 Vehicle: Seed = 1174190226

8.1.5.3 PRE-FACE Missing Data Imputation

The same procedure will be used for the analyses based on proportion of PRE-FACE item 1 (pimples) and item 5 (embarrassment) successes as the IGA success. Specifically, missing PRE-FACE items 1 and 5 values from which the dichotomized versions are derived will be estimated by MCMC. The pattern of missing observations in each treatment group cannot influence the missing value estimation in the other because the imputation is being conducted independently for each treatment group.

The missing PRE-FACE items 1 and 5 values will be derived for the analysis using the method of MCMC multiple imputation. Multiple imputation and subsequent analysis will involve 3 principal tasks:

1. Create a data set, one for each treatment group, of patients with observed values and those needing estimation by MCMC. The missing PRE-FACE items 1 and 5 values in each data set will be filled in using the MCMC method 5 times to generate 5 data sets. The resulting data sets for each treatment arm will be combined into one complete data set by imputation.

Syntax:

```
proc mi data=datain out=dataout seed=&seed. nimpute=5 <options>;  
  where trtpn=(1, or 2);  
  mcmc chain=multiple;  
  var baseline week2 week4 week8 week12;  
run;
```

2. For each complete data set, the dichotomous success rate (at least a 4-point reduction from Baseline) will be computed. The estimated global values will be rounded to the nearest integer value prior to evaluating the success rate. Each complete data set will be analyzed with a logistic regression with factors of treatment group and analysis center.
3. The results from these analyses will be combined into a single inference using SAS PROC MIANALYZE.

The following 4 random seeds have been pre-specified by using a random number generator:

- PRE-FACE Pimples Scores; S6G5T-3: Seed = 1597410322
- PRE-FACE Pimples Scores; S6G5T-3 Vehicle: Seed = 466920922

- PRE-FACE Embarrassment Scores; S6G5T-3: Seed = 288784276
- PRE-FACE Embarrassment Scores; S6G5T-3 Vehicle: Seed = 1746263137

8.1.5.4 Medication Date Imputation

If the medication start date is incomplete, then it will be imputed as follows for the purpose of determining concomitant use:

- If the start date is completely missing, the start date will be equal to the first dose date. However, if the stop date is not missing and is before the first dose date, then the stop date will be used instead.
- If the start day is missing, the first day of the month will be used.
- If the start day and month are missing, then the first day of the first month (January) will be used.

If the medication stop date is incomplete, then it will be imputed as follows for the purpose of determining concomitant use:

- If the stop date is completely missing and the medication is not ongoing, the stop date will be equal to the last dose date or date of completion/withdrawal, whichever is the latest.
- If the stop day is missing, the last day of the month will be used.

If the stop day and month are missing, then the last day of the last month (December) will be used.

